**Data Analysis**—The basic trial design consists of one between-participant effect (customary Fit and Strong! vs. Fit and Strong! Plus) and one within participant effect (time) variable. Although the structure of the study is factorial, data analysis will be based on the general linear mixed model in a regression format (this approach is

more flexible than traditional ANOVA). Because the same persons will be measured repeatedly, the conventional regression assumption regarding independence of error terms is untenable. There are two ways to deal with this problem: generalized estimating equations (GEE) and random effect models. GEE is simpler but requires more power and a stronger set of assumptions regarding missing data. Random effect models can be used to analyze longitudinal data and permit a more sophisticated approach to analyses than GEE at the cost of some additional complexity. The basic model for data analysis is

$$Y_{it} = \beta_0 + \beta_1 Plus_i + \beta_2 Time_{it} + \beta_3 Plus_i * Time_{it} + \beta_4 ARA_i + u_i + e_{it}$$

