**Missing Data.** Because we use longitudinal covariates to control on items like pain, in many cases missing data can be treated as “ignorable,” meaning that dropout will be missing at random (MAR) conditional on covariates and prior state. However, we will use “pattern mixture models” (Little, 1993; Hedeker and Gibbons, 1997) to explore the sensitivity of estimates to missing data assumptions. Specifically, we will include the observation pattern for each case in the model via dummy variables, interact those dummies with design variables, and compute a weighted average of the effects for the design variables based on the missing data problems. This method will allow us to assess what the effects of the design variables would have been, had all participants remained in the study.

**Power Analysis.** Based on prior work ([name] et al., 2010), we used software developed by Hedeker et al. (1999) to obtain sample size estimates. Assuming a 2-tailed test, a relatively small effect size of .2 (based on a five percent end point difference in mean weight and a linear pattern of change over time), 5% attrition at each time point, and a cross time correlation for weight of .9, we find that we need a sample size of approximately 300 subjects to detect an effect size of .2 (a 5% reduction in weight) at the end of the study with power = .9. In general, power estimates of this kind are not strongly affected by assumptions regarding attrition. However, we will enroll **400** subjects in order to maximize power.

**Timeline.** The timeline outlining all activities associated with the project is shown in Appendix C. It demonstrates that we will be able to achieve all of the tasks described within the **5**-years of the study.

**Methodological Considerations.** The proposed study has many strengths, including a large sample of high-risk older adults, an innovative integration of evidence-based weight loss approaches with Fit and Strong!, and potential for broad dissemination. However, as with any study, the design has some constraints (Table 6).

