**Table 6. Design Considerations**

Design Decisions	Rationale for Decision
1. Fit and Strong! plus is shorter than interventions in the literature.	Our goal is to incorporate common elements from longer interventions into one that is translatable. We include experts in weight loss intervention trials ([name]) and dietary assessment ([name]) in this effort. Fit and Strong! Plus has the same number of diet sessions (16) as the ADAPT diet/PA arm but in a format that is scalable.

2. We propose to recruit 400 older adults.	To meet this goal, we will use multiple strategies that succeeded in our prior work. We will set and closely monitor recruitment benchmarks and search for new community partners in this effort if needed.
3. We plan to follow participants for 24 months.	Our team has a 90% retention rate at 18 months. We will set retention targets and closely monitor success in meeting them. We will provide participant incentives and a lottery/cash voucher at each posttest, and we will conduct posttests at intervention sites in participants' neighborhoods.
4. Interventions are delivered by multiple instructors at multiple sites.	Our team has experience conducting training and conducting treatment fidelity checks for intervention trials. We have an established protocol to monitor fidelity and will extend this expertise to the new Fit and Strong! Plus intervention. A multi-instructor, multi-site approach will provide a more realistic assessment of feasibility for moving to scale.
5. Unanticipated consequences.	We have condensed the PA content of customary Fit and Strong! to reduce redundancy and allow space for new diet/weight loss content. We believe it unlikely that the changes will reduce the impact on PA maintenance and outcomes previously seen in Fit and Strong! trials. However, we will monitor this issue closely through fidelity checks and also use two-tailed tests to examine unexpected consequences of these changes.

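### The pattern-mixture sensitivity analysis averages arm effects within dropout patterns, so it omits the part of the treatment difference that comes from unequal dropout between arms

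*Combined protocol and SAP*

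**What the plan says.** The Data Analysis section describes a design with "one between-participant effect (customary Fit and Strong! vs. Fit and Strong! Plus) and one within participant effect (time) variable". Its basic model is a random-intercept regression in which the Plus-by-Time coefficient carries the treatment comparison.

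The Missing Data paragraph treats dropout in many cases as missing at random, given covariates and prior state. It then adds pattern-mixture models to "explore the sensitivity of estimates to missing data assumptions". The mechanics are that dummies for each participant's pattern of observed visits enter the model, and the analyst will "interact those dummies with design variables, and compute a weighted average of the effects for the design variables based on the missing data problems". The result is said to show "what the effects of the design variables would have been, had all participants remained in the study".

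The paragraph does not say whether the weights are pooled or specific to each arm, how patterns are grouped, or how a trend is carried past the last visit. The Power Analysis paragraph assumes "5% attrition at each time point", as one rate for both arms. Table 6 cites past experience, again without a split by arm: "Our team has a 90% retention rate at 18 months".

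**The concern.** What the text averages is one arm contrast per dropout pattern. What it claims to deliver is a contrast of everyone randomised. These are different quantities. Pattern membership is decided after randomisation and can depend on the arm, so comparing arms within a pattern treats a post-randomisation outcome as if it were a baseline stratum.

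Unequal dropout is plausible here, though nothing in the documents shows it. Only Plus participants have calorie targets, food diaries, weekly weigh-ins and calls that ask for their weight. If Plus loses more of the people who do not lose weight, the within-pattern contrasts can look the same while the randomised groups differ. The error can go in either direction.

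**Working it through.** **Inputs.** From the documents: visits at 0, 2, 6, 12 and 18 months; 5% attrition per time point; a cross-time correlation of 0.9; a target difference of 5% of weight, equated to 0.2 SD. Four post-baseline visits give 1 - 0.95^4 = 1 - 0.8145 = 18.5% lost by 18 months. Assumed, because the documents give none: dropout by arm, and the change in dropouts. Changes are percentages of body weight at the end of the study, and a negative arm difference favours Plus.

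**Algebra.** Use two patterns, with D = 1 for dropouts. Let b be the arm effect in completers, b + g1 the arm effect in dropouts, and g0 the dropout-minus-completer change in the customary arm.

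- Everyone randomised: b + p_Plus × g1 + (p_Plus - p_Cust) × g0.
- Average of within-pattern arm effects, with weight w on dropouts: b + w × g1.

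The term in g0 appears in no within-pattern arm effect. If g1 = 0, every choice of w returns b, so no choice of weights can recover the term.

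**Example 1: no arm effect within patterns.** Assumed dropout is 23.5% in Plus and 13.5% in customary (mean 18.5%). Completers change by -5% and dropouts by 0% in both arms.

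- Truth: 0.765 × (-5) - 0.865 × (-5) = -3.825 + 4.325 = +0.50.
- Average of within-pattern effects: 0 for any weights.
- Omitted term: 0.10 × 5 = 0.50.

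**Example 2: a real effect.** Same dropout; completers -5% in Plus and -1% in customary, dropouts 0%.

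- Truth: 0.765 × (-5) - 0.865 × (-1) = -3.825 + 0.865 = -2.96.
- Average with pooled weights: 0.815 × (-4) + 0.185 × 0 = -3.26.
- With the dropout rates reversed, the truth is 0.865 × (-5) - 0.765 × (-1) = -4.325 + 0.765 = -3.56. The pooled average is still -3.26.

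**Range for Example 1.** A 6-point dropout gap with dropouts at -1% gives 0.06 × 4 = 0.24. A 13-point gap with dropouts at +2% gives 0.13 × 7 = 0.91. Against the 5% target this is 0.24/5 = 5% to 0.91/5 = 18%.

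**Does the sensitivity analysis move away from the main result?** The table gives the expected estimate from the basic model (linear time, exchangeable correlation 0.9), with dropouts assumed last seen at 2, 6 or 12 months.

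| Case | Main model (2 / 6 / 12 months) | Pooled pattern average | Truth |
|---|---|---|---|
| Example 1 | +0.01 / +0.06 / +0.24 | 0 | +0.50 |
| Example 2 | -3.99 / -3.89 / -3.54 | -3.26 | -2.96 |
| Example 2, rates reversed | -4.00 / -3.96 / -3.83 | -3.26 | -3.56 |

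In Example 2 the check moves 0.73, 0.63 or 0.28 points towards the truth, out of a bias of 1.03, 0.93 or 0.58. With the rates reversed it moves in the right direction and overshoots by 0.30. In Example 1 it gives no useful warning.

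**Equal dropout.** With 18.5% in each arm and arm effects of -0.2 SD in completers and +0.2 SD in dropouts, the truth is 0.815 × (-0.2) + 0.185 × 0.2 = -0.126 SD. One simulated data set of 8,000 participants gave -0.195 from the main model and -0.125 from the pooled pattern average. Single runs of this kind carry an error of about 0.01 to 0.04.

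**The case against.** The strongest reply is that the text never commits to pooled weights. Time is a design variable too, so the planned model already contains what is needed to build arm-specific trajectories, and the cited method sources may intend that. This stands in part: the weights are undefined, and the -3.26 above is one reading. It does not rescue the wording, because the paragraph averages effects, and Example 1 fails for every set of weights. The remedy needs a different order of operations, averaging within arm before taking the difference.

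A reader might infer that the analysis is blind to informative dropout, or bound to confirm the main result. The documents do not support that. The stated purpose is sensitivity to missing-data assumptions in general, and the table shows clear movement whenever arm effects differ between dropouts and completers.

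A reader might also infer that the trial expects unequal dropout. It does not say so. Incentives, phone or home posttests and calls after missed sessions are described without distinction by arm. At 90% retention, a 13-point gap would mean about 16.5% against 3.5%, which is extreme.

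The size is also modest relative to sampling error. If 5% is 0.2 SD, the SD is 5/0.2 = 25% of weight. With correlation 0.9, 400 participants and 5% attrition per visit, the standard error of the arm difference is about 1.05 points, so 0.24 to 0.91 is about 0.2 to 0.9 standard errors. That is a fair limit on the importance of the point. It does not remove it, since a systematic omission is not averaged out.

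**Conclusion.** The point holds in a limited form. As written, the pattern-mixture analysis does not estimate the quantity the Missing Data paragraph assigns to it. It omits the dropout-share difference times the dropout-minus-completer change, and this term vanishes if dropout is equal by arm or if change does not differ by pattern. Under the assumed inputs of Example 1 the omission is 0.24 to 0.91 percentage points, or 5% to 18% of the 5% target; in Example 2 it is 0.30 points in either direction. All arm-specific dropout rates and dropout changes are assumptions. Only a sensitivity analysis is affected. It remains informative about arm effects that vary by pattern, but gives no useful warning when the problem is unequal dropout alone.

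**What to change.** Rewrite the averaging step. From the same pattern-by-arm-by-time model, compute pattern-specific trajectories in each arm, average them with that arm's own observed pattern proportions, and only then take the arm difference. Obtain the standard error by the delta method or bootstrap, so that the estimated proportions are included. Tabulate pattern proportions by arm beside the result, and state how patterns are grouped and how trends are carried past the last visit, which the averaging step does not settle.

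The cost is a few sentences in the plan, a little post-estimation code and a slightly larger standard error. No new data are needed and the primary analysis does not change.

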**Table 6. Design Considerations**

Design Decisions	Rationale for Decision
1. Fit and Strong! plus is shorter than interventions in the literature.	Our goal is to incorporate common elements from longer interventions into one that is translatable. We include experts in weight loss intervention trials ([name]) and dietary assessment ([name]) in this effort. Fit and Strong! Plus has the same number of diet sessions (16) as the ADAPT diet/PA arm but in a format that is scalable.

2. We propose to recruit 400 older adults.	To meet this goal, we will use multiple strategies that succeeded in our prior work. We will set and closely monitor recruitment benchmarks and search for new community partners in this effort if needed.
3. We plan to follow participants for 24 months.	Our team has a 90% retention rate at 18 months. We will set retention targets and closely monitor success in meeting them. We will provide participant incentives and a lottery/cash voucher at each posttest, and we will conduct posttests at intervention sites in participants' neighborhoods.
4. Interventions are delivered by multiple instructors at multiple sites.	Our team has experience conducting training and conducting treatment fidelity checks for intervention trials. We have an established protocol to monitor fidelity and will extend this expertise to the new Fit and Strong! Plus intervention. A multi-instructor, multi-site approach will provide a more realistic assessment of feasibility for moving to scale.
5. Unanticipated consequences.	We have condensed the PA content of customary Fit and Strong! to reduce redundancy and allow space for new diet/weight loss content. We believe it unlikely that the changes will reduce the impact on PA maintenance and outcomes previously seen in Fit and Strong! trials. However, we will monitor this issue closely through fidelity checks and also use two-tailed tests to examine unexpected consequences of these changes.

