*Eighty-five percent of participants in our effectiveness trial were overweight or obese at baseline, and many requested more help with diet and weight management than the curriculum currently offers. We propose to address this need by examining the feasibility, efficacy, and effectiveness of an intervention that combines an evidence-based PA program (Fit and Strong!) with elements of two evidence-based dietary programs (ADAPT and ORBIT). Several elements of the proposed study are highly innovative: 1) We will address a serious gap in the armamentarium of tools currently available to address the critical problem of obesity among older adults with LE OA. We will fill this gap by incorporating an evidence-based weight management protocol into the Fit and Strong! health education curriculum using intervention content and methods from both the ADAPT and ORBIT trials. Co-PI [name], recently completed the NCI-funded Obesity Reduction Black Intervention Trial (ORBIT) (CA105051). ORBIT tested the impact of a PA/diet intervention on obese middle-aged African American women. Using SCT and dietary change, ORBIT achieved a 5% reduction in weight at 6 months that was maintained at 18 months, very similar to the ADAPT findings ([name] et al., 2010). 2) The proposed PA/dietary intervention is scalable, and we have the experience and capacity to bring it to scale. We have demonstrated consistent benefits from Fit and Strong! across time, multiple geographic sites, instructors, and populations. The combination of this program with elements of effective dietary interventions in community-based settings has substantial potential to address the lack of scalable, efficacious PA/dietary interventions for older adults with OA. Further, our 8-week Fit and Strong! program benefits LE pain, stiffness and function using the same WOMAC and 6-minute distance walk measures used by ADAPT, but in half the time which is important for adoption purposes (Green & Glasgow, 2006). As the NIA Midwest Roybal Center for Health Promotion and Translation, we have the capacity to bring Fit and Strong! Plus to scale quickly if it demonstrates efficacy. We have developed instructor training protocols, an interactive website that tracks attendance and participant outcomes ([www.fitandstrong.org](http://www.fitandstrong.org)), Participant and Instructor Manuals, and standard procedures to monitor program fidelity in the field. We also have a Roybal Advisory Committee that includes representatives from several groups that are key to translation of EB programs, both locally and nationally (see Appendix A for Committee Roster). A recent review of 19 weight loss studies found that very few addressed issues of translation into real world settings and urged that future studies address how programs will be adopted and maintained with special attention to costs for participants and for program implementation (Akers, Estabrooks and Davy, 2010). 3) We now test the impact of dietary change as a route to weight loss out to 24 months in contrast to 18 month outcomes reported by current studies. 4) We will examine health care claims data and health-related quality of life pre and post both interventions. Fit and Strong! is currently being considered for inclusion in a Centers for Medicare and Medicaid Services (CMS) evaluation of appropriateness for Medicare reimbursement. The CMS data will enable us to examine impact of both programs on health care use and cost. 5) We will conduct the trial in local Park Department sites. Parks and Recreation*

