will be repeated 4 times at 3 sites to achieve a final targeted baseline sample of 400 participants (i.e., 2 interventions x 3 sites x 4 replications x 17 participants = 408 participants). Outcome measures will be obtained at baseline, 2, 6, 12 and 18 months (see Figure 2, Projected Consort Flow Diagram, Appendix C).

**Settings**—We will partner with the Chicago Park District and Westside Health Authority (WHA) to conduct the trial. Although we require 3 sites to conduct the trial, the Park District has identified 4 sites that can participate, and WHA has identified 1 site. The Park sites include Smith Park (Northwest), Wicker Park (Northwest), Washington Park (Southeast), and Columbus Park (Southwest), and the WHA site includes their location on the westside (see more information about the sites in Appendix D). **All sites are staffed by nationally certified exercise instructors who will be trained separately to conduct either customary Fit and Strong! or Fit and Strong! Plus. (See letters from [name], CEO, Chicago Park District from [name], CEO, National Recreation and Park Association, and from [name], CEO, Westside Health Authority in Section 14).**

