**Procedures and Data Collection**—We have experience training research staff for health risk reduction interventions and will use the same procedures we have used in the past. Training will take place prior to the initial interview and will cover an overview of the study, informed consent, interviewing skills, data check/editing, anthropometrics, participant contact (phone call etiquette and schedule for mailings), protocol for compensating participants, data scanning, and data packet construction. **Prior to the pilot we developed an interviewer training manual covering all data collection procedures (see Training Manual, Appendix E).** Project staff will obtain informed consent at the baseline interview. Participants will be paid \$25 per interview for each of 5 interviews. In addition, four participants at each participating site (2 from each study group) who complete each posttest will be randomly selected to receive a \$50 gift certificate to a local store of their choice. Participants will also be paid \$50 for participating in 24-month interviews. CRHA staff will make at least 10 attempts to schedule interviews on different days of the week and at different times of the day before giving a case a final disposition. Posttest measurement *will take place at intervention sites* and will be scheduled on separate days for the two intervention groups.

Additionally, if participants complete data collection for the ancillary study (Protocol # 2013-0098) prior to their baseline/post-test interview, the height and weight data collected by the ancillary study will be used as part of the #2012-0277 study. Protocol # 2013-0098 has received approval through March 19, 2014. The study is called, "Effect of Community-based Lifestyle Interventions on Serum Biomarkers of Cancer Risk in Overweight and Obese Older Minority Adults with Osteoarthritis: A Randomized Trial". The data collection site for this protocol is the Integrative Physiology Lab in the UIC Disability, Health & Social Policy Building, at [name].

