***Participants in Fit and Strong! Plus meet with the instructor during week 6 to develop a negotiated PA plus weight management maintenance contract. The instructor uses the same process model as in Fit and Strong! to arrive at a realistic diet/weight loss maintenance plan. The review includes strategies to 1) include more fruits and vegetables daily, 2) decrease consumption of fat, 3) decrease sugar sweetened beverages, and 4) decrease overall caloric consumption by dealing with triggers, selecting healthy snacks, making shopping plans, etc. The review can include referral to community programs like Weight Watchers if participants express a preference for ongoing structured group-based reinforcement. In cases of both Fit and Strong! and Fit and Strong! Plus our goal is to enroll participants who are at high risk of mobility disability, help them adopt healthy behaviors over 8 weeks, and then help them to develop personalized maintenance strategies that have substantial probability of long-term adherence.***

**Maintenance boosters**—Maintenance of behavior will be reinforced in both groups during months 3 through 24 using tapered TR. Using methods tested in our effectiveness trial ([name] et al., 2010), we will recruit 2 Master's of Public Health student research assistants (RAs) well versed in health education techniques. One student will work with customary Fit and Strong! participants, and the other will work with Fit and Strong! Plus participants using scripted protocols. RAs will be trained separately. A two-week training program will include 1) reading materials related to successful PA or PA and weight loss maintenance interventions; 2) an overview of intervention objectives; 3) a review of each week's curriculum; and 4) role playing dealing with frustrations and barriers inherent in achieving physical activity or physical activity / weight loss maintenance. The Project Manager will meet with RAs bi-weekly to debrief calls, provide feedback and guidance, and revise the protocols as needed. To monitor call quality, she and the study PIs will listen to a sample of calls made by each RA periodically. All participants will receive one call during months 4, 8, and 15. Newsletters will be mailed each quarter to study participants. The newsletter will reinforce materials learned in class about physical activity and diet related topics.

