**Table 3: Proposed Study Measures**

**A. Screening Measures**

10-item Short Portable Mental Status Questionnaire (Kahn et al., 1960)	
 
• Screens for moderate-to-severe cognitive impairment
 
• Good reliability and validity (Kane and Kane, 1981)
 
• Ineligible if answer more than three items incorrectly
 

Physical examination of joints and muscles by study rheumatologist	
 
• Determines clinical presence of OA in LE joints
 
• Rates functional significance using ACR arthritis functional class (Hochberg et al., American College of Rheumatology, 1992)
 

History of falls	
 
• Self-reported number of falls in last 2 years (Mobility and aging survey developed and used by the Centers for Disease Control and Prevention Healthy Aging Network).
 

B. Dependent Measures: Assessed at baseline, 2, 6, 12 and 18 months	
Primary Proximal Outcomes	
National Cancer Institute (NCI) Percent Energy from Fat Screener (Thompson et al., 1998)	
 
• Assesses usual daily intake from fat over previous 12 months
 
• Correlates strongly with true dietary intake (Thompson et al., 2007)
 

NCI Fruit and Vegetable Screener (Thompson et al., 2000)	
 
• Obtains fruit and vegetable intake during a typical day
 
• Correlates strongly with true dietary intake (Thompson, 2002)
 

Block Brief Food Frequency Questionnaire (FFQ) (Block et al., 1990)	
 
• Assesses 6-month changes in energy intake, % energy from fat, saturated fat, grams of fiber, servings of fruit and vegetables based on 70 food items
 
• Reliability and validity demonstrated in a wide range of age, gender, income and ethnic groups including low-income women (Coates et al., 1991; Block et al., 1992; Lanza et al., 2001; French et al., 2000)
 

Primary Distal Outcomes	
Weight and BMI	
 
• Weight measured without shoes using same calibrated Tanita BWB-800 digital scale
 
• Height measured without shoes to calculate BMI using Seca 214 portable stadiometer
 

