**Health-Related Quality of Life.** The EQ-5D assesses 5 dimensions of health-related quality-of-life: mobility, self-care, usual activities, pain/discomfort, and anxiety/depression (EuroQoL, 1990). Respondents rate each dimension on 3 levels: no problems, some problems, extreme problems. The EQ-5D can be used to translate scores into Quality-Adjusted Life Years (QALYs) for cost analyses. **Witham and Avenell (2010) also recommend the inclusion of these measures in future diet trials with older adults.**

**Technology Usage:** Participants will complete questions regarding technology use during the baseline outcomes assessment. We are trying to assess if they have internet access and if they utilize it to search for health or medical information online. We will obtain this information from the participants during their baseline outcome assessments. We would like to provide health-related website links for their reference during the program and maintenance period. In addition, it will allow us to create future projects related to health information and technology use.

**Blood Pressure:** Blood pressure will be assessed using the NHANES protocol. Readings will be obtained at baseline, 2, 6, 12, and 18 month follow-up visits. Participants with blood pressure over 180/110 mm Hg or below 90/50 mm Hg will be asked to contact their physician immediately after the reading and ask for instructions for care. If the participant's physician cannot be reached then an ambulance will be called for the participant. Participants with readings in these ranges will not be eligible to participate in the study.

**Mediators**—We will measure variables related to self-efficacy, social support, intrinsic motivation, and barriers to weight loss as outlined in Table 4 at all timepoints.

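### Weight loss is said to be tested out to 24 months, but every visible outcome schedule, including the one for weight and BMI, stops at month 18

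*Combined protocol and SAP*

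**What the plan says.** Three statements set a 24-month horizon for follow-up or for weight loss.

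- Item 3 of the Innovation section: "We now test the impact of dietary change as a route to weight loss out to 24 months in contrast to 18 month outcomes".
- Table 6, row 3: "We plan to follow participants for 24 months". The rationale beside it cites the team's retention of 90% at 18 months.
- Procedures and Data Collection: a $50 payment "for participating in 24-month interviews", on top of $25 "per interview for each of 5 interviews".

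Four places set the outcome schedule, and all end at month 18.

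- Approach, design paragraph before Settings: "Outcome measures will be obtained at baseline, 2, 6, 12 and 18 months".
- Table 3, heading of part B: "Dependent Measures: Assessed at baseline, 2, 6, 12 and 18 months". Weight and BMI sit under this heading as primary distal outcomes.
- Blood Pressure paragraph: "Readings will be obtained at baseline, 2, 6, 12, and 18 month follow-up visits".
- Table 5 (RE-AIM), Maintenance cell: maintenance of change, with weight loss named, is assessed at 12 and 18 months. The same cell plans interviews about sustainability but gives them no date.

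Two further places bear on the point. The Power Analysis sets its 5% weight target at the end of the study and names no month. The Health Care Utilization paragraph describes a 36-month Medicare claims period made of 12 months before and 18 months after baseline.

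**The concern.** Weight is a primary outcome, and follow-up beyond 18 months is one of the five innovations that the plan claims for itself. A test at 24 months needs weight measured at 24 months. If the listed schedule is the whole schedule, the last observation entering the mixed model is at month 18. The fitted Plus-by-Time slope could be projected to month 24, but a projection is not a test, and whether weight loss holds between months 18 and 24 is the question that the innovation claim raises. Staff working from Table 3 would not know to weigh participants at the 24-month interview, and an analyst working from the Data Analysis section would not know whether a sixth wave belongs in the model.

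**Working it through.** **1. The statements side by side**

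| Place | Last month | What is attached to it |
|---|---|---|
| Innovation, item 3 | 24 | test of dietary change as a route to weight loss |
| Table 6, row 3 | 24 | follow-up of participants |
| Procedures and Data Collection | 24 | a paid interview, content not given |
| Approach, design paragraph | 18 | outcome measures |
| Table 3, part B | 18 | all dependent measures, including weight and BMI |
| Blood Pressure paragraph | 18 | blood pressure |
| Table 5, Maintenance | 18 | mediators, diet, weight loss, OA symptoms |

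These are all current text; none comes from a log of changes.

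**2. Interviews against waves.** The listed waves are months 0, 2, 6, 12 and 18, a count of 5. The standard payment covers 5 interviews, so each standard interview matches one listed wave. The 24-month interview is paid separately, which gives 5 + 1 = 6 contacts, of which 5 have listed measures. The payment text therefore confirms a contact at month 24 but assigns it no measure.

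**3. Size of the gap.** 24 − 18 = 6 months, and 6 / 24 = 25% of the stated follow-up has no listed outcome wave.

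**4. Power statement.** Its inputs are a two-tailed test, an effect size of 0.2 (5% of weight), linear change over time, 5% attrition at each time point, a cross-time correlation of 0.9, power 0.9 and about 300 participants, with 400 to be enrolled. Neither the final month nor the number of time points is among them. On the listed waves the last is month 18; on the Innovation text it would be month 24. No sample-size calculation is needed for this point.

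**5. Claims period (exploratory).** The stated total is 36 months. The stated parts give 12 + 18 = 30, which is 36 − 30 = 6 months short. A total of 36 would need 12 + 24.

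**The case against.** The strongest reply is that the 24-month interview may itself be a measurement visit. Procedures and Data Collection uses the word interview for the measurement visits and ties height and weight data to the baseline and post-test interviews. On that usage, the schedule lists may simply not have been updated. Parts of the Approach section were removed from the text available for this review, and Appendix C, with the flow diagram and timeline, is not shown; either could define a month-24 wave. This stands, and it limits the point. A reader might infer that weight at 24 months will not be collected. The documents support only that it is not listed. The reply does not remove the conflict: if a month-24 wave is defined elsewhere, the design paragraph and Tables 3 and 5 are incomplete; if it is not, the Innovation text and Table 6 overstate the horizon.

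Three other inferences go too far.

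- The Maintenance boosters paragraph says "Maintenance of behavior will be reinforced in both groups during months 3 through 24 using tapered TR", which might be read as promising a 24-month outcome. It describes telephone reinforcement, with calls in months 4, 8 and 15, and not outcome measurement, so it is not counted as evidence here.
- A reader might infer that the sample size is wrong. Under linear change, an effect of 0.2 at month 24 would be 0.2 × 18 / 24 = 0.15 at month 18. But the visible text does not say that the target applies at month 24, and it states neither the alpha level nor the correlation structure. No shortfall is shown.
- Unequal claims windows might be said to bias the cost results. The Data Analysis section plans only exploratory patterns and trends between and within groups, and both arms share the same window. The figure of 18 carries a stray hyphen, so an editing or text-conversion slip is plausible.

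**Conclusion.** The inconsistency is real. The plan states a 24-month horizon for weight loss and for follow-up, and pays for a 24-month contact, while all four visible outcome schedules end at month 18 and none lists a measure at month 24. As listed, the schedule cannot support the claimed 24-month test of weight loss; the difference is 6 months, or 25% of the stated follow-up. That the visible statements conflict is certain. That nothing is measured at month 24, and that no month is fixed for the power target, holds only for the visible text. The change should be made because it touches a primary outcome and a headline claim. The claims-period mismatch (36 against 30) is minor and adds no weight to this conclusion.

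**What to change.** State one final outcome month and use it throughout. There are two ways to do this.

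- Restate the weight-outcome horizon in Innovation item 3 and Table 6 row 3 as 18 months, and say what the 24-month interview is for. This is a text change only. Its cost is the claimed advantage over 18-month studies, which has to be dropped.
- Or list at least weight at the 24-month interview in the design paragraph, Table 3 part B and Table 5, and add that wave to the mixed model in the Data Analysis section. The contact is already paid for, so the cost is one more measurement and one more wave in the model.

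Under either choice, name the same month in the Power Analysis for the 5% weight target. In the Health Care Utilization paragraph, correct the total or the windows so that they agree.
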